The goal of medical therapy in HCV is to achieve sustained virologic response (SVR) defined as prolonged clearance of HCV RNA. Until recently, treatment of HCV consisted of combination therapy of a weekly injection of a pegylated interferon and oral ribavirin.

There are six types of HCV genotype; the viral genotype is integral in determining appropriate treatment regimens, with genotype 1 being particularly difficult to treat successfully. Less than 50% of genotype 1 patients achieve a sustained viral response (SVR) with standard peginterferon-ribavirin. Boceprevir and telaprevir were the first HCV protease inhibitors to be approved for the treatment of HCV genotype 1. These drugs must be used in combination with pegylated interferon (triple therapy) plus ribavirin to maximize efficacy and prevent the emergence of resistance-associated variants (Ferenci, 2011).

Treatment related toxicity is the primary limiting factor in HCV interferon-based therapy with significant side effects necessitating dose reductions in almost half of treated patients and discontinuation in nearly a third of all patients (National Institutes of Health Consensus, 2002). Thrombocytopenia is a dose and/or therapy-limiting side effect in patients with HCV receiving interferon-based therapies. Thrombocytopenia may be a result of antiviral treatment, but may also develop as a complication of chronic HCV infection, unrelated to antiviral treatment.

In patients with HCV, thrombocytopenia occurs most commonly in those with advanced liver disease and cirrhosis. In such patients, thrombocytopenia render patients ineligible for antiviral treatment and requiring dose reductions or discontinuation and may also prevent patients from having liver biopsies and other invasive procedures, thereby hampering a physician's ability to stage and monitor the patient's liver condition. Until recently, the treatment options for thrombocytopenia in HCV affected patients were limited to intravenous immunoglobulins, corticosteroids, platelet transfusions, and cytokines, and in severe cases, splenectomy.

REVOLADE (eltrombopag)

REVOLADE (eltrombopag; GlaxoSmithKline, Research Triangle Park, NC, USA) is an oral, non-peptide, thrombopoietin receptor (TPO-R) agonist that interacts with the TPO-R and induces differentiation of hematopoietic stem and progenitor cells to megakaryocytes.

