8.3.4. On label and off label definitions

If information on splenectomy, prior medication use, and contraindications for surgery is available, then use of eltrombopag for a patient will be categorized into the following groups:

- On-label use:
 - patient is an adult, has a diagnosis of chronic ITP, has been splenectomized or has a contraindication for surgery, and has received prior corticosteroids, immunoglobulins therapy; or
 - o patient is an adult, has a diagnosis of chronic HCV, has clinically meaningful thrombocytopenia limiting interferon-based therapy, and date of eltrombopag is after REVOLADE approval date (September 2013).
- Off-label use:
 - o patient is an adult, has chronic ITP, but has not received prior corticosteroids, immunoglobulins therapy or has not been splenectomized and does not have a contraindication for surgery;
 - o patient is an adult, has HCV, but does not have clinically meaningful thrombocytopenia limiting interferon-based therapy or the date of REVOLADE is prior to REVOLADE approval date;
 - o patient is an adult, but does not have ITP or HCV;
 - o patient is < 18 years of age

If there is no information on splenectomy, prior medication use, and contraindications for surgery, then classification will be more general:

- On-label use:
 - o patient is an adult and has a diagnosis of chronic ITP; or
 - o patient is an adult and has a diagnosis of HCV with clinically meaningful thrombocytopenia limiting interferon-based therapy, and date of eltrombopag after REVOLADE approval date
- Off-label use:
 - o patient is an adult, but has acute rather than chronic ITP;

- o patient is an adult, but does not have ITP and does not have HCV with clinically meaningful thrombocytopenia or has clinically meaningful thrombocytopenia limiting interferon-based therapy but date of eltrombopag is prior to REVOLADE approval date;
- o patient is an adult, but does not have ITP or HCV; or
- o patient is < 18 years of age

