8.6.3. File Retention and Archiving

To enable audits from regulatory authorities or GSK, the investigator must agree to keep records, including the identity of all participating patients, all original signed informed consent forms (ICFs), patient screening logs, copies of all eCRFs (which will be provided by sponsor at study end), source documents and adequate documentation of relevant correspondence. The records should be retained by the investigator. The records must be available for review in the event the site is selected for monitoring, audits, or inspections and must be safely archived following the study conclusion, according to local regulations or as specified in the contract, whichever is longer. In the event that archiving of the file is no longer possible at the site, the site will be instructed to notify GSK.

8.7. **Data Analysis**

8.7.1. **DUS Analyses**

This is a multinational, retrospective, observational, medical chart review study. A Statistical Analysis Plan (SAP) describing the detailed statistical methodology and analysis will be provided as a separate document.

Continuous variables will be reported as mean, standard deviation, median and range. Categorical variables will be summarised as number and proportion of the total study population (counting missing data as a class), and by subgroups if and where appropriate. Confidence intervals (as 95% CI) will be calculated using the method outlined by Newcombe (Newcombe, 1998) for the key variables.

Participating physicians

Number of participating physician, and practice setting, will be summarized descriptively.

Page 126

Patient demographics and disease characteristics

Descriptive statistics will be given for the variables below:

- Age at time of initial REVOLADE prescribing dose
- Gender
- Race/Ethnicity
- Relevant medical history for applicable conditions

REVOLADE Patient characteristics

Number and percentage of the following categories will be described and stratified if number permits according to the dates of new indication approval:

- Adult chronic ITP patients
- Adult patients with HCV and clinically meaningful thrombocytopenia
- Patients < 18 years with chronic ITP
- Patients < 18 years with HCV (with and without thrombocytopenia)
- Patients < 18 years without chronic ITP or HCV but with another disease type, by specific disease type
- Adult patients with cancer, by cancer type
- Adult patients with myelodysplastic syndrome/AML

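### In section 8.3.4 the fallback off-label HCV line omits the interferon condition, so adults with HCV and meaningful but non-limiting thrombocytopenia are neither on-label nor off-label

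*Protocol*

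**What the plan says.** Section 8.3.4 of the protocol has two sets of definitions. The detailed set applies when the relevant history is available. For HCV it treats adult use as off-label if the patient lacks meaningful thrombocytopenia that limits interferon-based therapy, or if treatment predates the HCV approval.

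The fallback set is triggered as follows: "If there is no information on splenectomy, prior medication use, and contraindications for surgery, then classification will be more general". Its lines for adults are:

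- On-label, ITP: "patient is an adult and has a diagnosis of chronic ITP; or"
- On-label, HCV: the patient "has a diagnosis of HCV with clinically meaningful thrombocytopenia limiting interferon-based therapy, and date of eltrombopag after REVOLADE approval date"
- Off-label, ITP: "patient is an adult, but has acute rather than chronic ITP"
- Off-label, HCV, first limb: "patient is an adult, but does not have ITP and does not have HCV with clinically meaningful thrombocytopenia"
- Off-label, HCV, second limb: the patient "has clinically meaningful thrombocytopenia limiting interferon-based therapy but date of eltrombopag is prior to REVOLADE approval date"
- Off-label, other: neither ITP nor HCV

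Patients under 18 are off-label in both sets. Neither set has a residual or unclassifiable category.

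**The concern.** The fallback on-label HCV line and the second off-label limb both require that the thrombocytopenia limits interferon-based therapy. The first off-label limb does not mention interferon. It excludes everyone who has HCV with meaningful thrombocytopenia, whether or not interferon treatment is at issue. The on-label and off-label lines are therefore not complements, and a group of patients falls between them.

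The trigger adds to the problem. It rests partly on splenectomy and contraindications to surgery, which play no part in the HCV criteria. Gaps in chart data that are irrelevant to the HCV label could help move an HCV patient from off-label to no class at all.

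What is at stake is the off-label proportion. Section 8.5.1 sizes the study on its precision, and section 8.2.4 says the data will be used to judge whether prescribing follows the labelling.

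**Working it through.** **Plan's own figure.** Section 8.5.1 gives a precision of 2.1% for a 5% off-label rate with 400 patients. The half-width is 1.96 × √(0.05 × 0.95 / 400) = 0.0214, giving 2.9% to 7.1%. It reproduces and is not in dispute. It does presuppose that every off-label user can be counted.

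**Logic check.** Take an adult with chronic HCV and no ITP. Meaningful thrombocytopenia may be absent, present but not limiting interferon-based therapy, or present and limiting. The start date may be before or after the HCV approval. That gives 3 × 2 = 6 cells.

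| Thrombocytopenia | Start date | Detailed set | Fallback set |
|---|---|---|---|
| Not meaningful | before | off-label | off-label (first limb) |
| Not meaningful | after | off-label | off-label (first limb) |
| Meaningful, not limiting | before | off-label | **none** |
| Meaningful, not limiting | after | off-label | **none** |
| Meaningful, limiting | before | off-label | off-label (second limb) |
| Meaningful, limiting | after | on-label | on-label |

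For the two unclassified cells, the fallback lines fail one by one:

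- both ITP lines fail, because the patient has no ITP;
- the on-label HCV line fails, because the thrombocytopenia is not limiting;
- the first off-label limb fails, because the patient does have HCV with meaningful thrombocytopenia;
- the second limb fails, because it needs limiting thrombocytopenia;
- the line for neither ITP nor HCV fails, because the patient has HCV;
- the age line fails, because the patient is an adult.

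The result is the same whether the second limb is read as qualified by the absence of ITP or as standing alone. If the interferon condition is inserted in the first limb, both cells become off-label and all six agree with the detailed set.

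**Size.** The documents give no count, so this is illustrative. Assume 20 true off-label users among 400 (20/400 = 5.0%), of whom k fall into the gap.

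| k | Kept in denominator | Removed from denominator |
|---|---|---|
| 1 | 19/400 = 4.75% | 19/399 = 4.76% |
| 2 | 18/400 = 4.5% | 18/398 = 4.52% |
| 4 | 16/400 = 4.0% | 16/396 = 4.04% |

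Section 8.7.1 keeps missing values as a class within the total study population, which points to the first column. It does not say that a patient who meets no definition is handled that way. The proportion falls in either case.

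**The case against.** The strongest reply is that few patients can reach the gap. Read as written, the trigger needs all three kinds of history to be absent. Section 8.3.2 collects preceding treatment for every patient, previous antiviral therapy for HCV patients, splenectomy status and comorbidities that may rule out surgery. An HCV chart with any of these does not literally meet the trigger. Section 8.2.5 also expects very few HCV patients. This stands, and it limits the size of the effect. It does not remove the contradiction between the two sets.

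A second reply is that the intended rule is obvious from the other HCV lines and that a statistical analysis plan can tidy it up. The intention is indeed fairly clear. But the protocol does not leave this definition open. It states two rules that disagree, and an analyst would have to depart from one of them.

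Three stronger readings are tempting but not supported:

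- A reader might infer that the study cannot show whether HCV use follows the label. The detailed set classifies this use as off-label, and sections 8.3.2 and 8.3.3 collect indication, antiviral treatment and platelet counts, so the class can be recovered.
- A reader might count every HCV patient treated without an interferon link as lost. That assumes all of them are in the fallback set. The share that is there is not given.
- A reader might object that the section 8.7.1 row "Adult patients with HCV and clinically meaningful thrombocytopenia" also lacks the interferon condition. That list groups patients by disease and age. Its adult chronic ITP row likewise mixes on-label and off-label use, so the row is not a label classification.

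The background in section 6.1 notes that thrombocytopenia "may also prevent patients from having liver biopsies and other invasive procedures". This makes use unconnected with interferon conceivable, but it does not say that REVOLADE is given for that purpose or how often.

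**Conclusion.** The point holds as a minor definitional error. In the fallback set, an adult without ITP who has HCV and meaningful but non-limiting thrombocytopenia has no class, while the detailed set calls the same patient off-label. The direction is certain: any such patient lowers the off-label proportion. The size is unknown and probably small. The fall from 5.0% to between 4.75% and 4.0% rests on an assumed 20 true off-label users in 400 and an assumed 1 to 4 lost. Neither number of patients is a forecast from the documents.

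**What to change.** Either of two wording changes in section 8.3.4 is enough:

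1. Carry the condition *limiting interferon-based therapy* into the first limb of the fallback off-label HCV line.
2. Apply the detailed HCV rule to all HCV patients, whatever is known about splenectomy or surgery, and use the two-tier switch for ITP only. This also removes the dependence on history that is irrelevant to HCV.

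With either, state that patients whose interferon link is not documented form a separate unclassifiable class, counted as neither on-label nor off-label, and report their number.

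The cost is a few words in one section. No new data items are needed, because indication, antiviral treatment and platelet counts are already collected. The unclassifiable class may hold only a handful of patients. Section 8.7.1 needs no change on this account.

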8.4. Data Sources

This study is a retrospective medical chart review. Local site staff will review the medical chart of each enrolled patient and extract the data.

These data will be entered pseudonymised into the eCRF via secure web-based EDC system.

8.5. Study Size

8.5.1. Sample Size for the DUS

300 to 450 patients, enroled by approximately 18-21 sites will be recruited for participation in this study. It is planned to recruit all patients who are willing to participate, from all certified physicians in certified centers in all participating EU countries, and without a minimum designated for any country based on the estimated availability of eligible patients from the medical records within the planned recruitment period.

We provide hereafter the level of precision i.e., width of the 95% confidence interval (CI) for various sample sizes and proportions. Table 1 presents the precision in the estimate of the tentative proportion of use of REVOLADE out of the labelled indication for tentative proportions of 2, 3, 4 and 5% and different sample sizes.

2013N177706_00 **CONFIDENTIAL** WEUKBRE7133

Table 1 Precision of estimation for proportions of 2, 3, 4 and 5% of off-label use and increasing sample size

[figure not shown]
	Tentative proportions of REVOLADE off-label use											
	0.02			0.03		0.04			0.05			
Sample Size Patients	CI Width	L95%	U95%	CI Width	L95%	U95%	CI Width	L95%	U95%	CI Width	L95%	U95%
200	0.019	0.001	0.039	0.024	0.006	0.054	0.027	0.013	0.067	0.03	0.02	0.08
400	0.014	0.006	0.034	0.017	0.013	0.047	0.019	0.021	0.059	0.021	0.029	0.071
600	0.011	0.009	0.031	0.014	0.016	0.044	0.016	0.024	0.056	0.017	0.033	0.067

CI: 95% confidence interval; L: lower bound; U: upper bound.

Table 1 and Figure 2 show that the width of the 95% CI decreases as sample size increases; samples greater than 500 patients enable the estimation of the proportion of off-label use with an acceptable degree of precision. Increasing the sample size beyond 600 patients has minimal effect on the width of the 95% CI.

A sample size of 400 patients will allow the detection of a rate of 5% of off-label use with a precision of 2.1%, that is, the estimated proportion will be between 2.9% and 7.1%.

Figure 2 Confidence interval for tentative proportions of 2, 3, 4 and 5% and increasing sample size

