- All platelet counts ($x10^9/L$) at the time of primary medical condition, at initiation of REVOLADE, and dates, and resulting in dose change, by dose
- REVOLADE exposure (start date, stop date, doses)
- If REVOLADE discontinued, date and reason for discontinuation

Data Sources

This study is a retrospective medical chart review. Local site staff will review the medical chart of each enroled patient and extract the data.

These data will be entered pseudonymised into the eCRF via a secure web-based EDC system.

Study Size:

300 to 450 patients, enroled by approximately 18-21 sites will be recruited for participation in this study. It is planned to recruit all patients who are willing to participate, from all certified physicians in centers in selected EU countries, and without a minimum designated for any country, based on the estimated availability of eligible patients from the medical records within the planned recruitment period. Samples greater than 400 patients enable the estimation of the proportion of off-label use with an acceptable degree of precision. A sample size of 400 patients will allow the detection of a rate of 5% of off-label use with a precision of 2.1%, that is, the estimated proportion will be between 2.9% and 7.1%.

Data Analysis:

A Statistical Analysis Plan (SAP) describing the detailed statistical methodology and analysis will be provided as a separate document.

Continuous variables will be reported as mean, standard deviation, median and range. Categorical variables will be summarised as number and proportion of the total study population (counting missing data as a class), and by subgroups, where appropriate. Confidence intervals (as 95% CI) will be calculated using the method outlined by Newcombe (Newcombe, 1998) for the key variables.

All computations and generation of tables, listings and figures will be performed using SAS 9.1.3 or higher (SAS Institute, Cary, NC, USA) statistical software.

Estimated Milestones

- Final protocol submitted to the PRAC: October 2013
- Protocol approved with PRAC comments received: January 2014
- Sign Off of the updated protocol: May 2014
- Submission to the EU-PAS register: June 2014
- Start of data collection: September 2014
- End of data collection: 8 months after start of abstraction, April- May 2015
- Final study report: October 2015, i.e., 6 months after end of abstraction/study collection

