8.2.5. Patient Enrolment

Since the purpose of this study is to evaluate routine clinical use of REVOLADE, patients will be identified based on the prescription of REVOLADE rather than on a specific diagnosis or condition.

The study population will consist of patients who have been prescribed REVOLADE for whatever reason according to the data retrieved in the medical records, provided they gave informed consent, had not or were not currently participating in a REVOLADE clinical trial, and used REVOLADE within the time period defined below. The medical records of all patients treated with REVOLADE in a participating centre will be reviewed for inclusion in this retrospective study, until the overall target number of at least 300 patients has been reached, irrespective of indication, medical condition, dose and treatment duration.

Patients are eligible for inclusion in study if their first prescription of REVOLADE was given between the period immediately after REVOLADE launch date and the start date for data abstraction i.e., September 2014. Patients who have been first prescribed REVOLADE after September 2014 will not be included in the study in order to ensure that study procedures do not influence prescribing practices. Informed consent will be

obtained as per country-specific regulations. Assuming the country-based first launched dates of REVOLADE in its initial chronic ITP indication (see Figure 1), the eligibility periods in the three selected countries thus span between January 2011 and September 2014 for France, April 2010 and September 2014 for Germany and December 2010 and September 2014 for Spain.

The earliest launch date for the chronic HCV-associated thrombocytopenia indication in these countries can be no sooner than September 2013, corresponding to the date it was approved by the European Commission. Considering that approval of HCV-associated thrombocytopenia indication was just recently, the number of expected HCV-associated thrombocytopenia patients therefore will be very small.

It is expected that approximately six or seven sites will be identified per country, and that up to 50 medical records will be abstracted at each site accounting for a total of 300 to 450 patients for the study.

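### The study-size text calls precision acceptable above 400 patients in one place and above 500 in another, for a plan of 300 to 450, and Table 1 labels half-widths as widths

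*Protocol*

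**What the plan says.** Protocol section 8.5.1 plans the size as follows: "300 to 450 patients, enroled by approximately 18-21 sites will be recruited for participation in this study". It then sets out the "level of precision i.e., width of the 95% confidence interval (CI) for various sample sizes and proportions" and draws up Table 1 "for tentative proportions of 2, 3, 4 and 5% and different sample sizes". The sizes tabulated are 200, 400 and 600.

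From Table 1 and Figure 2, section 8.5.1 concludes that "samples greater than 500 patients enable the estimation of the proportion of off-label use with an acceptable degree of precision". The abstract (section 3, Study Size) says: "Samples greater than 400 patients enable the estimation of the proportion of off-label use with an acceptable degree of precision". Both places give the same worked example, which 8.5.1 words as "A sample size of 400 patients will allow the detection of a rate of 5% of off-label use with a precision of 2.1"%. Both add that the estimate will lie between 2.9% and 7.1%.

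On when enrolment ends, section 8.2.5 has records reviewed "until the overall target number of at least 300 patients has been reached". Section 8.9.1 foresees a stop at circa 300 to 450 patients or at the end of abstraction, whichever is earlier.

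**The concern.** The two threshold sentences are almost word for word the same, yet one says 400 and the other 500. Both are current text, since no amendment has been issued. Neither gives a numeric criterion for acceptable precision, so nothing in the protocol shows which figure is meant.

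Nor does the plan fit either figure. Its upper end lies below 500 and its lower end below 400. The precision quoted is for 400, a size at which the plan does not commit to stop, and neither end of the planned range appears in Table 1.

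The label adds a second error: what the text and the column heading call the width of the interval is half of it.

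Precision for the off-label proportion is the only statistical justification given for the study size. As written, a reader cannot tell from it what interval to expect, or whether the plan meets the protocol's own standard.

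**Working it through.** **Inputs.** Planned size 300 to 450 (sections 3, 8.1, 8.2, 8.2.5, 8.5.1, 8.9.1). 95% two-sided interval, so z = 1.96. Off-label proportions 2% to 5%, with 5% in the worked example (8.5.1). Thresholds: above 400 (section 3) and above 500 (8.5.1).

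**Formula.** Normal-approximation half-width h = 1.96 × √(p(1 − p)/n); limits p ± h.

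**The plan's own figure.** With p = 0.05 and n = 400: h = 1.96 × √(0.0475/400) = 1.96 × 0.0109 = 0.0214, limits 0.0286 and 0.0714. This is the stated 2.1%, 2.9% and 7.1%. All 12 combinations of size and proportion in Table 1 reproduce in this way to the printed rounding.

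**The same formula at p = 0.05 for the sizes that matter:**

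| n | Half-width | 95% limits | Full width | Above 400? | Above 500? |
|---|---|---|---|---|---|
| 300 | 0.0247 | 0.025 to 0.075 | 0.049 | no | no |
| 400 | 0.0214 | 0.029 to 0.071 | 0.043 | no | no |
| 450 | 0.0201 | 0.030 to 0.070 | 0.040 | yes | no |
| 500 | 0.0191 | 0.031 to 0.069 | 0.038 | yes | no |

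The interval at 300 is √(400/300) = 1.155 times as wide as at 400, so about 15% wider. In half-width the differences are 2.47 − 2.14 = 0.33 points (300 against 400) and 2.01 − 1.91 = 0.10 points (450 against 500).

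**Where 2.1% is met.** A half-width that rounds to 2.1% or less needs n of at least 1.96² × 0.0475/0.0215² = 394.7, so 395 patients. The upper part of the plan, 395 to 450, delivers it; 300 to 394 does not.

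**The label.** For n = 400 and p = 0.05, Table 1 prints 0.021 under 'CI Width' beside limits of 0.029 and 0.071. Those limits are 0.071 − 0.029 = 0.042 apart (0.043 before rounding), twice the printed entry. The same holds, within rounding, for every entry in the column.

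**The case against.** The strongest reply is that no calculation fails. The 2.1% is stated for 400 patients, 400 lies inside the plan, and 450 does slightly better. All of this stands. A reader might infer that the design does not deliver the stated precision, but the documents support only that it is not guaranteed.

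A reader might also infer that the study cannot reach acceptable precision and must be enlarged. That does not follow. The text says that larger samples enable acceptable precision, not that smaller ones preclude it, and no numeric standard is set. The 500 may be a leftover figure, since the worked example beside it uses 400. In a descriptive study with no hypothesis test, differences of 0.1 to 0.33 points change no decision. Section 8.2.3 also allows recruitment to be extended if targets look out of reach. These points limit the consequence, but they do not reconcile 400 with 500 or either with 300 to 450.

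On the label, both limits are printed beside every entry, so few readers would be misled. It is still wrong by the table's own figures. Figure 2 is not available here and may cover 300 and 450, so the remark about missing sizes applies to Table 1 only.

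Two further inferences should not be drawn:

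- **Interval method.** Section 8.7.1 cites a comparison of seven methods, whereas Table 1 uses the normal approximation. Naming the variant can be left to the SAP, and the effect is small. With a Wilson interval (an assumption), 400 patients at 5% give 3.3% to 7.6%, a half-width of 2.17 against 2.14 points.
- **Off-label use far above 5%.** The strict rule in 8.3.4 might suggest this, but the protocol gives no such rate, calls its proportions tentative, and applies that rule only where the needed data are available.

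**Conclusion.** The point holds as an inconsistency in the study-size justification together with a mislabelled column. Every planned size falls short of the 8.5.1 threshold, and sizes from 300 to 400 also fall short of the abstract's. At 5% off-label use the plan gives a half-width of about 2.5 points at 300 and 2.0 points at 450, around a quoted 2.1 that is right at 400. If abstraction ends below 300, as 8.9.1 permits, the interval is wider still.

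These figures use the normal approximation and treat patients as independent, as Table 1 does. The numerical effect is modest. The text should be corrected because it is the stated basis for the study size.

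**What to change.** 1. In section 3 and section 8.5.1, replace the 400 and 500 statements with one common statement for the 300 to 450 plan: expected 95% confidence interval half-width of about 2.0 to 2.5 points at 5% off-label use, wider if abstraction ends below 300.
2. Add rows to Table 1, keeping the 2% to 5% columns. Half-widths for 2, 3, 4 and 5%: 0.016, 0.019, 0.022, 0.025 at n = 300, and 0.013, 0.016, 0.018, 0.020 at n = 450.
3. Relabel the 'CI Width' column as half-width, and correct the sentence in 8.5.1 that equates precision with the width of the interval.
4. In both places, present 2.9% and 7.1% as the expected 95% confidence interval at 400 patients, not as limits within which the estimate will fall.

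Higher off-label proportions may be added if marked as assumptions, but they are not part of this correction. The cost is a text and table edit. Sample size, data collection and analysis are unchanged, and the precision quoted at the lower end of the plan becomes slightly less favourable.

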8.9.1. Study closure/uninterpretability of results

The planned study closure is October 2015, time of the final report. Medical records will be abstracted until April 2015 unless patients discontinue or withdraw from the study. It is foreseen that study enrolment will stop upon reaching circa 300-450 patients or at the end of abstraction whichever comes first.

The study can be terminated at any time for any reason by GSK. The investigator may be informed of additional procedures to be followed in order to ensure that adequate consideration is given to the protection of the patient's interests. The investigator will be responsible for informing IECs of the early termination of the study. The early termination of the study is considered a major amendment; therefore, the relevant competent authorities will be notified before a final decision is made and approval for termination is granted.

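### Section 8.5.1 and the Abstract give different sample sizes for acceptable precision (above 500 and above 400), and the planned 300 to 450 patients are reconciled with neither

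*Protocol*

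**What the plan says.** The protocol makes two kinds of statement about study size.

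**Size judged to give acceptable precision**
- Section 8.5.1, below Table 1: "samples greater than 500 patients enable the estimation of the proportion of off-label use with an acceptable degree of precision".
- Abstract, Study Size: "Samples greater than 400 patients enable the estimation of the proportion of off-label use with an acceptable degree of precision".

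**Size planned**
- Section 8.5.1: "300 to 450 patients, enroled by approximately 18-21 sites will be recruited for participation in this study". The Abstract and sections 8.1 and 8.2 give the same range.
- Section 8.2.5: records are reviewed "until the overall target number of at least 300 patients has been reached". The same section later expects a total of 300 to 450.
- Section 8.9.1: "study enrolment will stop upon reaching circa 300-450 patients or at the end of abstraction whichever comes first".

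Section 8.5.1 describes its precision measure as the "width of the 95% confidence interval (CI) for various sample sizes and proportions" and tabulates it "for tentative proportions of 2, 3, 4 and 5% and different sample sizes". The rows of Table 1 are 200, 400 and 600. The single worked example, given in both the Abstract and section 8.5.1, reads "A sample size of 400 patients will allow the detection of a rate of 5% of off-label use with a precision of 2.1" per cent, which the protocol spells out as 2.9% to 7.1%. No numeric limit for acceptable precision is stated. Section 4 records no amendments, so both thresholds are current text.

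**The concern.** One sentence appears twice with two different numbers, and neither number is tied to a target half-width. A reader cannot tell which of the two governs. The planned range lies wholly below one of them and mostly at or below the other, so the text never says why 300 to 450 is enough.

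The off-label proportion is the quantity on which the size is justified, and this is a precision-based descriptive study with no other quantitative planning claim. A study that stops at 300 would follow the protocol, yet its report could not point to any sentence that supports that size or states its precision. Sections 8.2.3 and 8.9 also make extra recruitment time, sites or countries depend on whether patient targets look reachable. It should therefore be clear whether the target is 300 or a range up to 450.

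**Working it through.** **Inputs.** Confidence level 95% and assumed proportions 2% to 5% (section 8.5.1); planned sizes 300 to 450 (Abstract, 8.1, 8.2, 8.5.1, 8.9.1); earliest target-based stop 300 (8.2.5); thresholds 400 (Abstract) and 500 (8.5.1).

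**Step 1: reproduce the protocol's figure.** The Wald half-width is h = 1.96 × √(p(1 − p)/n). For p = 0.05 and n = 400:

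h = 1.96 × √(0.0475/400) = 1.96 × 0.01090 = 0.0214, so the interval is 2.9% to 7.1%.

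This is the stated 2.1 points. All 12 precision entries of Table 1 (three sizes, four proportions) reproduce to rounding in this way. The column headed as CI width therefore holds half-widths.

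**Step 2: same formula at the planned sizes and at 500.**

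| n | h at 5% (points) | interval at 5% | h at 2% (points) |
|---|---|---|---|
| 300 | 2.47 | 2.5% to 7.5% | 1.58 |
| 400 | 2.14 | 2.9% to 7.1% | 1.37 |
| 450 | 2.01 | 3.0% to 7.0% | 1.29 |
| 500 | 1.91 | 3.1% to 6.9% | 1.23 |

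**Step 3: compare.**
- 300 against 500: √(500/300) = 1.29, so the half-width is 29% larger; at 5% the difference is 2.47 − 1.91 = 0.56 point.
- 300 against 400: √(400/300) = 1.155, about 15% larger; at 5% the difference is 2.47 − 2.14 = 0.33 point.
- 450 against 400: 2.01 against 2.14, so the upper end of the plan is slightly better than the worked example.

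**Step 4: set the plan against the two thresholds.**
- Above 500 (section 8.5.1): no size from 300 to 450 qualifies.
- Above 400 (Abstract): 401 to 450 qualifies; 300 to 400 does not.
- A stop at 300 is above neither.

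**Step 5: sensitivity to the interval method.** Section 8.7.1 says the analysis intervals will follow a cited paper that, by its title in the reference list, compares seven methods. The protocol does not say which one is meant. If it is the Wilson score interval (an assumption), an observed 5% gives 3.05% to 8.08% at 300 (half-width 2.52 points) and 3.34% to 7.42% at 450 (2.04 points). The half-widths hardly change, but the limits shift upwards. At 400 the Wilson limits are 3.3% to 7.6%, so Table 1 was not built with that method.

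**The case against.** The strongest reply is that a sentence saying samples above a certain size enable acceptable precision gives a sufficient condition, not a minimum. On that reading the two sentences can both be true, and nothing in the protocol calls a smaller sample unacceptable. Section 8.5.1 itself goes on to use 400 as its worked example. The study is descriptive, and the difference in precision is small. Much of this stands, and it rules out several stronger readings.

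- A reader might infer that the protocol has declared its own size inadequate. It has not: no target half-width and no lower limit are stated. The fault is an inconsistent and unexplained standard.
- A reader might infer that the whole plan falls short. That is so only against 500; sizes 401 to 450 are above the Abstract's 400.
- A reader might infer that the study closes at 300. Section 8.2.5 says at least 300 and expects up to 450, and section 8.9.1 gives a range. So 300 is the earliest target-based stop, not the fixed final size.
- A reader might infer that section 8.5.1 nowhere shows precision at 300, 450 or 500. Only the rows of Table 1 can be judged. Figure 2 is not reproduced in the text at hand and may cover those sizes.
- A reader might infer a calculation error. There is none.

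What the reply does not remove is that one sentence carries two numbers, and that neither is reconciled with the planned range.

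**Conclusion.** The point holds as an internal inconsistency in the study-size justification. It should be fixed, but it does not threaten the study: no estimate, classification or analysis changes. The largest gap at issue, 300 against 500 patients at 5% off-label use, is about 0.6 point of half-width; against the worked example at 400 it is about 0.3 point.

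These figures assume a true proportion of 5%, the Wald formula behind Table 1, and patients treated as independent. They are expected precision, not a guarantee. The proportion may differ, and section 8.9.1 also lets enrolment end when abstraction ends, which could leave fewer than 300.

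**What to change.** 1. In the Abstract and section 8.5.1, delete both thresholds and put one statement in their place, for example: *If off-label use is 5%, the expected 95% CI half-width is about 2.5 points with 300 patients and about 2.0 points with 450.* Word it as expected under the assumed proportion.
2. Add rows for 300 and 450 to Table 1 and label the column as half-width. Preferably compute the table by the interval method chosen for the analysis, and name that method.
3. Align section 8.2.5 with the 300 to 450 target used in the Abstract and in sections 8.1, 8.2, 8.5.1 and 8.9.1. Say plainly whether review continues beyond 300.

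The cost is a few sentences and two table rows. No additional patients, sites or data are needed. The only concession is that the precision stated for the lower end becomes about 2.5 points where the reader now sees only 2.1.
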